6.2.3 Exploratory endpoints

To identify risk factors for CMV reactivation, we will first build univariate generalized linear regression models to test the association between CMV reactivation and different potential risk factors identified in Section 1 C.2. We will also build multivariate Generalized Linear Models for association with CMV reactivation, by including (i) factors found significant at level 0.2 in the first step and (ii) all risk factors, and then using a step-wise backward selection using the Akaike Information Criterion (AIC) or the Bayesian Information Criterion (BIC) for model selection.

We will use descriptive statistics and plots to examine the association of CMV viral load kinetics in blood and lung compartments with RSFDs and VFDs, mortality at day 28 and 180, duration of respiratory support in survivors, PaO₂/FiO₂, and static respiratory system compliance. We will also build regression models (generalized linear models) to examine these relationships more closely. We will also descriptively determine the sensitivity and specificity of the rapid lateral flow CMV serostatus assay, and assess its concordance with the standard clinical assays, using Cohen's kappa statistic.

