4. Duration of mechanical ventilation (among survivors) by day 28.
5. Duration of respiratory support (among survivors) by day 28.
6. Oxygenation ($\text{PaO}_2/\text{FiO}_2$ ratio) daily on study days 1–7.
7. ICU-free days by day 28.
8. CMV DNA detection in plasma and endotracheal aspirate (ETA) by day 28 (>0 IU/mL, >1000 IU/mL).
9. Number of patients with reportable adverse events of Grade 3 or higher by day 28.

Exploratory Objectives:

1. To evaluate whether static respiratory system compliance at randomization, day 4, and day 7 differs between ganciclovir recipients and placebo recipients.
2. To assess the occurrence of invasive bacterial and fungal infections in ganciclovir recipients compared to placebo recipients.
3. To evaluate whether organ dysfunction scores (regular SOFA variables, including respiratory, coagulation, liver, cardiovascular, CNS, and renal function, with the Sat/FiO_2 ratio replacing the

PaO₂/FiO₂ ratio used in the standard SOFA score) differ between ganciclovir recipients and placebo recipients.

4. To assess long-term life quality as measured by the Acute Respiratory Failure Core Outcome Measurement Set (COMS), which will include the Katz Index of Independence in Activities of Daily Living (ADL) and Lawton – Brody Instrumental Activities of Daily Living Scale (IADL) completed by legally authorized representatives (LARs) or participants at baseline; and the ADL, IADL, Hospital Anxiety and Depression Scale (HADS), EQ-5D-5L, and Impact of Events Scale – Revised (IES-R), completed by patients at day 180.
5. To assess risk factors associated with CMV reactivation kinetics, including demographics, comorbidities, severity of illness, organ dysfunction, lymphocyte count, time from hospital admission to enrollment, ventilation type, viral load prior to randomization, and duration of illness before hospital admission.
6. To characterize the relationship between CMV viral load kinetics in blood and lung compartments and respiratory-support-free days (RSFDs), ventilator-free days (VFDs), and secondary clinical outcomes, including oxygenation, static respiratory system compliance, mortality, and duration of mechanical ventilation in survivors.
7. To assess the performance of a rapid lateral flow CMV serostatus assay compared to clinically performed assays for CMV IgG antibodies, as conducted in CLIA-approved laboratories, throughout the study and at trial completion.

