2.5 Use of ganciclovir in the context of respiratory failure

2.5.1 Ganciclovir antiviral therapy decreases CMV-associated lung injury in a murine model.

Studies in a murine CMV sepsis model (cecal ligation and perforation) demonstrate that in mice with latent CMV infection, CMV reactivation during sepsis causes lung injury (fibrosis) [45, 46]. Ganciclovir prophylaxis prevents the development of lung fibrosis after lung injury in this model by blocking murine CMV reactivation [45]. This effect is dependent on both the dose and timing of antiviral therapy, providing strong evidence of a mechanistic link between CMV reactivation and lung injury (**Figure 2-5**), consistent with improvement of lung-related outcomes with ganciclovir prophylaxis in our phase 2 GRAIL RCT.

[figure not shown]
Figure 2-5. Ganciclovir Decreases Sepsis-associated Pulmonary Fibrosis (Represented by Percent of Pixels) in Mice: Effect of Dose and Duration [45]

2.5.2 Phase 2 RCT: Efficacy of ganciclovir for preventing CMV reactivation in patients with sepsis-associated acute respiratory failure.

Our phase 2 GRAIL RCT showed that ganciclovir was effective in suppressing CMV reactivation (**Figure 2-6**). Specifically, CMV was suppressed in plasma and endotracheal aspirate (ETA) and bronchoalveolar lavage fluid (BAL). Safety data for this trial are detailed in Section 3.6.1.7. Similar success in preventing CMV reactivation was observed in a single-center, open-label RCT of valganciclovir for CMV seropositive, critically ill patients [47].

Figure 2-6. Cumulative Incidence of any CMV Reactivation and High-Grade CMV Reactivation in Plasma through Day 28 [23].

2.5.3 Phase 2 trial results demonstrate that ganciclovir prophylaxis improves several respiratory clinical outcomes in critically ill patients with sepsis-associated acute respiratory failure.

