Figure 2-8. Baseline patient variables are not predictive of CMV reactivation in critically ill patients with sepsis, in the absence of ganciclovir treatment.^a Data represent odds ratios for binary CMV responses (cross-sectional). Transfusion status was also not associated with CMV reactivation (data not shown).

^a After adjustment for age, race, gender, baseline transfusion status, study cohort, and a standardized score created from APACHE II and III scores used in the individual studies.

positive. Standard enzyme-linked immunosorbent assays (ELISA) are routinely available, but the turnaround time varies by laboratory, and can require up to 48-72 hours. Delays in receiving results increase the likelihood that CMV reactivation has already occurred. However, empirically treating everyone would lead to unnecessary exposure to ganciclovir in the ~40% of patients who are CMV seronegative (and thus not at risk for CMV reactivation and associated adverse effects). To address this challenge, we will utilize a new, investigational, easy to perform, rapid, lateral flow assay (LFA) for CMV IgG antibodies (QooLabs, Inc.). This technology is similar to that used for home pregnancy tests, and is easy to perform and interpret. The FDA has determined this to be a nonsignificant risk device study [Reference #Q202303]). All rapid testing results will be confirmed with a standard assay performed in a CLIA-certified lab. This approach will allow physicians to rapidly identify CMV seropositive patients in the ICU, so as to promptly initiate therapy.

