5.3.1 Exploratory Endpoints

1. Static respiratory system compliance at randomization, day 4 and day 7.
2. Invasive bacterial and fungal infections.
3. Organ dysfunction scores (regular SOFA variables including respiratory, coagulation, liver, cardiovascular, CNS and renal; as well as SpO₂/FiO₂ ratio).
4. The NHLBI-endorsed Acute Respiratory Failure Core Outcome Measurement Set (COMS) in survivors at day 180.
5. Risk factors for CMV reactivation (>0 IU/mL, >1000 IU/mL) in plasma and lung
 - a. Sex, age, race
 - b. Co-morbidity
 - c. APACHE III score at baseline
 - d. SOFA score and individual components
 - e. Lymphocyte count
 - f. Time from hospital admission
 - g. Viral load prior to randomization
6. Relationship of CMV viral load with RSFDs and VFDs and secondary clinical outcomes:
 - a. Viral load: initial, peak, slope, area under the curve (AUC)
 - b. Association with RSFD and VFD, day-28 mortality, duration of mechanical ventilation in survivors, static compliance, and PaO₂/FiO₂.
 - c. Baseline viral load in plasma and lung.

7. Viral load kinetics among survivors in day 7 and 14.
8. Sensitivity, specificity, PPV and NPV of rapid lateral flow CMV serostatus assay.
9. CMV cellular immunity, neutralizing antibodies, antibody epitope expansion, and transcriptional signatures.
10. Use of ECMO at any time during the post-randomization period, and duration if used
11. Occurrence of neuromuscular blockade.
12. Prone positioning status.

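### The CMV risk-factor and viral-load models in protocol 6.2.3 name no treatment term or arm restriction, although half the participants receive a drug meant to suppress reactivation

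*Combined protocol and SAP*

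**What the plan says.** Protocol 6.2.3 describes a first step in which "we will first build univariate generalized linear regression models to test the association between CMV reactivation and different potential risk factors". Multivariable models then take "factors found significant at level 0.2 in the first step and (ii) all risk factors", with backward selection by AIC or BIC. For viral load against RSFDs, VFDs, mortality, duration of support, oxygenation and compliance, descriptive summaries come first, and then "We will also build regression models (generalized linear models) to examine these relationships more closely".

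The endpoint in protocol 5.3.1 is "Risk factors for CMV reactivation (>0 IU/mL, >1000 IU/mL) in plasma and lung". The factors listed there are sex, age, race, co-morbidity, APACHE III, SOFA, lymphocyte count, time from admission and pre-randomization viral load. SAP section 2.2 states the matching objective: "To assess risk factors associated with CMV reactivation kinetics, including demographics, comorbidities, severity of illness, organ dysfunction, lymphocyte count", and so on. Treatment arm is in none of these lists. Section 6.2.3 itself takes its factors from a Section 1 C.2, which does not exist in this protocol's numbering.

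On the drug effect, protocol 2.5.2 states: "Our phase 2 GRAIL RCT showed that ganciclovir was effective in suppressing CMV reactivation". The team's earlier work was done in untreated patients. The caption of Figure 2-8 (risk factors) says "in the absence of ganciclovir treatment", and the caption of Figure 2-3 (reactivation and outcomes) carries the same qualification.

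**The concern.** Treatment is expected to be among the strongest determinants of reactivation in this trial, and the models for reactivation do not mention it. A model with one predictor has no room for it, and nothing forces it in at the multivariable step. Two consequences follow if all participants are analysed together.

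- **Risk factors.** The odds ratio becomes an average over a placebo arm in which reactivation is common and a ganciclovir arm in which it is suppressed. It no longer describes either group, and it is not comparable with the team's earlier estimates in untreated patients.
- **Viral load.** Peak, slope and AUC are measured after randomization and are affected by the drug. If ganciclovir also changes the outcome by another route, such as toxicity, a model without arm attributes part of that effect to viral load.

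At stake is how the exploratory results on who reactivates, and what reactivation does, are read.

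**Working it through.** The plan states no power or effect size for these models, so it has no figure to reproduce. The calculations below are illustrations.

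**Inputs**
- Allocation 1:1, 250 per arm (protocol 7.1 and protocol summary).
- Reactivation without ganciclovir about 40% (protocol 2.4.1, which also gives viremia of at least 30%).
- Reactivation on ganciclovir: not in the text, because the figure is not shown. Assumed 5%, 12% and 20%.
- Binary factor, prevalence 50%, independent of arm by randomization; true placebo-arm OR 2.0 (assumed).

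**Risk factors.** On placebo, the risks that average 40% with OR 2.0 are 0.3177 (factor absent) and 0.4823 (present): (0.4823/0.5177)/(0.3177/0.6823) = 2.0. In all participants, each risk is the mean of the two arms' risks, and the pooled OR is [p1/(1−p1)]/[p0/(1−p0)].

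| Ganciclovir rate | Same OR in both arms: p0, p1 | Pooled OR | No factor effect on ganciclovir: p0, p1 | Pooled OR |
|---|---|---|---|---|
| 5% | 0.1759, 0.2741 | 1.77 | 0.1839, 0.2661 | 1.61 |
| 12% | 0.2011, 0.3189 | 1.86 | 0.2189, 0.3011 | 1.54 |
| 20% | 0.2317, 0.3683 | 1.93 | 0.2589, 0.3411 | 1.48 |

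With 30% reactivation on placebo, the pooled ORs for the same three ganciclovir rates are 1.86, 1.93 and 1.98 (same OR) and 1.65, 1.55 and 1.47 (no effect on ganciclovir).

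In the same-OR case the shrinkage is non-collapsibility of the odds ratio, and an arm term restores 2.0. In the no-effect case an arm main effect alone does not recover the placebo-arm 2.0; that needs an arm-by-factor term or a placebo-arm estimate.

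**Power** for the factor, two-sided 0.05, difference in proportions, 40% on placebo: placebo only (125 per factor group) 76%. Pooled (250 per factor group), for ganciclovir rates of 5%, 12% and 20%: 75%, 85%, 92% with the same OR; 60%, 55%, 52% with no effect on ganciclovir.

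**Viral load.** Let reactivation (yes/no) stand in for peak, slope or AUC, and let RSFD = b × reactivation + d × arm, where d is the drug effect in days that does not pass through the virus. Leaving out arm shifts the estimate of b by

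d × [P(ganciclovir | reactivated) − P(ganciclovir | not reactivated)].

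- 5%: 0.05/0.45 − 0.95/1.55 = 0.111 − 0.613 = −0.50
- 12%: 0.12/0.52 − 0.88/1.48 = 0.231 − 0.595 = −0.36
- 20%: 0.20/0.60 − 0.80/1.40 = 0.333 − 0.571 = −0.24

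For d = −2 days (harm) the shift is +1.0, +0.7 and +0.5 day, so reactivation looks less harmful than it is. For d = +2 the signs reverse. For d = 0 there is no shift.

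**The case against.** Several points on the other side are sound.

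- **Pooling is inferred from silence.** Section 6.2.3 names no analysis population. SAP section 11 refers additional analyses to a companion exploratory SAP that is not available here and may settle the matter. This stands: a reader might infer that both arms are certainly pooled without arm, but 6.2.3 does not say so. Step 3 of the mediation analysis in protocol 6.2.2 does come close. It regresses RSFDs on viremia alone, in a sequence whose other steps use treatment as a predictor and so need both arms.
- **Treatment-adjusted models exist elsewhere.** Mediation step 4 includes both treatment and viremia. It covers RSFDs only and runs only if steps 1 to 3 are significant. Section 6.2.2 also plans multivariable models for secondary endpoints, which include CMV detection, adjusted for reactivation risk factors. These probably contain arm, but the text does not name the term, and they do not replace the 6.2.3 models.
- **The 0.2 screen does not by itself discard predictors.** A reader might infer that it does. Route (ii) starts from all risk factors, so the documents do not support that.
- **Pooling need not cost power.** With the same OR in both arms, pooled power is 75–92% against 76% for placebo only. Power falls only if the factor acts more weakly under ganciclovir. Making a placebo-only model the lead analysis is therefore debatable; including arm is not.
- **Confounding by arm is narrow.** Arm is randomized, so it cannot confound baseline factors or baseline viral load. It affects only post-randomization measures, and only if the drug acts on the outcome outside the viral pathway. SAP section 4 reports that enrollment was closed over safety and futility concerns, and SAP section 11 plans toxicity analyses. Such a route is plausible but not established.

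**Conclusion.** The point holds as a gap in the specification of exploratory models. As written, 6.2.3 models an outcome that the drug is meant to suppress without mentioning the drug. If all participants are used, the odds ratio is attenuated in every scenario examined. From 2.0 it falls to 1.77–1.93 with a common effect and to 1.48–1.61 with no effect under ganciclovir, given 40% reactivation on placebo, a factor present in half of participants and assumed ganciclovir-arm rates of 5–20%. Post-randomization viral-load associations move by 0.24–0.50 day per day of non-viral drug effect, a quantity that is unknown and may be zero.

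The documents do not support the broader conclusions that predictors will be lost, that power must fall, or that all viral-load associations are confounded by arm. Primary and secondary inferences are untouched. This is a cheap improvement.

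**What to change.** In protocol 6.2.3, and in the companion exploratory SAP if it is silent:

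1. State the analysis population, and force treatment arm into every risk-factor model, including the first-step models (which then hold arm plus one factor). Exempt arm from backward selection.
2. For the risk-factor models, also report an arm-by-factor term and the placebo-arm estimates. The latter are the ones comparable with the earlier work in untreated patients.
3. Force arm into every model that relates post-randomization viral load (peak, slope, AUC) to an outcome. Do not rely on mediation step 4 for this, since it is conditional and limited to RSFDs.
4. Replace the reference to Section 1 C.2 with the list in 5.3.1.

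The cost is a change of wording and a little more analysis. The interaction and placebo-arm estimates will be imprecise, the former because few reactivations may occur on ganciclovir; they should be reported with confidence intervals and read as exploratory.

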6.2.4 Other pre-specified analyses

Primary analysis, cITT, mITT, and survivors

Ideally, any patient randomized would be included in the conventionally defined ITT analysis cohort. Nonetheless in an emergency care setting, such as this study, the following unusual but important scenario will need to be considered: a patient is eligible and randomized but by the time of drug delivery no longer meets eligibility criteria and thus, should have been excluded.

Accordingly, it is intended that patients randomized but not having drug/placebo delivered will not be included in the primary analysis cohort. The integrity of randomization shall remain preserved, as the decision to deliver drug/placebo is determined a priori and completely independent of treatment assignment (14). If a participant is withdrawn from the study before a dose of study drug is given, no study procedures will be performed and no study data will be collected, and these participants will be excluded from the primary analysis. However, if a participant is withdrawn after receipt of study drug, safety procedures (e.g. monitoring of

creatinine and CBC with differential) will continue for another 48 hours, no study biosamples will be obtained, and study data in the medical record will continue to be collected per protocol (e.g. respiratory-support-free days), and they will be included in the primary analysis. In addition to the primary analysis, we will also conduct a randomized or classical ITT analysis, which will consider all patients randomized. This will be used as a conservative alternative to our primary comparison. Additionally, we will also perform 2 modified intent-to-treat (mITT) analyses: 1) excluding patients who were withdrawn from the study for any reason (including initial positive CMV LFA test followed with confirmatory negative CMV ELISA test) after receiving at least one dose of study drug, and 2) only including patients who survived and were followed to day 28. We will also test for an interaction of treatment period (pre and post drug use) and the primary treatment differences at the study conclusion. Finally, we will perform subgroup analyses evaluating treatment effect stratified on mode of respiratory support.

6.2.5 Post hoc analyses

Statistical considerations for the post hoc analyses described in Section 5.4 are described in the statistical analysis plan.

6.3 Randomization scheme

The randomization sequence will be uploaded by SCHARP into the Medidata's Randomization and Trial Supply Management (RTSM) system and provided to each site through Medidata. The randomization will be block-randomized by site. At each institution, the pharmacist with primary responsibility for drug dispensing is charged with maintaining the security of the randomization list. A research pharmacy designee may be provided access to the randomization assignment from Medidata RAVE.

6.4 Blinding

Participants and site staff (except for site pharmacists) will be blinded as to treatment arm assignments (e.g., study drug or placebo). Study drug assignments are accessible to those site pharmacists, contract monitors (or the central site IDS pharmacist as backup), and unblinded statisticians who are required to know this information to ensure proper trial conduct. Access to randomization assignment is restricted to unblinded statisticians only. Emergency unblinding if ever needed is managed 24/7 through Medidata RTSM. Any discussion of study drug assignment between the site clinical and pharmacy staff is prohibited. The DSMB members also are unblinded to treatment assignment to conduct review of trial safety. Thus, closed reports for the DSMB will include the treatment indicators of the two participant groups.

Unblinding procedures are discussed in Section 9.15.

6.4.1 Missing data

Every effort will be dedicated to complete, comprehensive, and accurate data collection and data annotation by the DCC. However, issues and challenges arise in every clinical trial. Due to the high proportion of deaths in this patient population, one major challenge in this RCT of which we must be aware and ready to correct is missing data. Missing data can occur to the primary endpoint and key secondary endpoints (e.g., CMV reactivation [missing viral load values] and organ dysfunction or the NHLBI-endorsed acute respiratory failure core outcome measurement set). We have carefully examined sources of missing data from the GRAIL phase 2 trial and adjusted the analysis plan accordingly.

6.4.1.1 Missing Data in Primary Outcome.

It is highly likely that missing data in RSFDs, the primary outcome in our RCT, will be MNAR (missing not at random), as most missingness will result from withdrawal of consent, a rare occurrence that can happen when patients and families are in crisis, and is more likely to occur in sicker patients. However, we only expect <3% missingness in our primary outcome (see Section 2A), and thus this data can be ignored from the primary analysis. However, if for some unforeseen reasons, missingness in RSFDs does increase beyond a set threshold of 5%, we will have to adjust for it in our analysis plan. In that case, we will use baseline patient characteristics identified in (1) under the Exploratory Objectives/Endpoints (Section 5.3) to model the missing data mechanism in RSFDs, which will be used to estimate the treatment effect unbiasedly using maximum likelihood methods, provided the missing data model is correctly specified.

6.4.1.2 Missing Data in some secondary outcomes due to Study Design.

The absence of data pertaining to some secondary endpoints (for example, static respiratory system compliance) may be problematic if participants are discharged from the ICU, are on pressure support after being extubated, or expire prior to our pre-specified time points for endotracheal aspirates and serum collection. For example, if the Ganciclovir intervention reduces duration of respiratory support, it may bias the results because participants cannot undergo endotracheal aspirate if they are extubated. Thus, to minimize missing data and to maximize the CMV detection rate, we have selected multiple time points for the endotracheal aspirate (Day 1 and twice weekly until Day 28). If these issues still occur, we will address them in the analysis phase using data imputation methods, or by acknowledging it as a limitation of any analyses conducted with these variables.

6.4.1.3 Missing Data in covariates.

Missing data can occur in covariates as well, due to factors such as death, withdrawal, or other reasons; this will need to be accounted for in our analyses, if overall missingness (in covariates) increases beyond 5%. Since we expect covariate missingness in this study to be MAR (missing at random), we will use weighting adjustments (for example, weighted generalized estimating equations) or multiple imputation methods [98, 99] to deal with covariate missingness.

